## **4.2 Study Population**

For entry into the study, the following criteria **MUST** be met.

### **4.2.1 Inclusion Criteria**

The following inclusion criteria are required for patient participation in the study:

1. At least 18 years of age
2. At least one contact allergen with a 2+ (strong) or 3+ (extreme reaction) confirmed by patch testing within 18 months of the baseline visit that can be duplicated at the initiation of the study (placement at Week 0 and patch test reaction read at Week 0 +72-120 hours).
3. Allergic contact dermatitis diagnosed clinically by the principle investigators who have expertise in allergic contact dermatitis
4. Investigator's global assessment score of at least 3 (range 0-4) at the screening and baseline visits
5. Documented recent history (within 18 months of patch testing) of inadequate response to treatment with topical medications and allergen avoidance
6. Able and willing to provide informed consent, participate in study visits, and undergo visit procedures.

### **4.2.2 Exclusion Criteria**

Any of the following exclusion criteria would prohibit patient participation in the study:

1. Prior dupilumab use
2. Treatment with a systemic immune-regulating medication within 3 months of the baseline visit or the patient's prior patch testing, whichever is longer. Examples of these medications include azathioprine, methotrexate, mycophenolate mofetil, Janus kinase inhibitors, and phototherapy (including tanning booths). Cyclosporine or prednisone may not have been used within 1 month of the baseline visit.
3. Treatment with other biologic agents, such as TNF inhibitors, anti-IL 17 agents, anti-IL 12/23 agents, or anti-IL 23 agents, within 4 months of baseline visit or the patient's prior patch testing, whichever is longer.

4. Use of rituximab within at 6 months (or until lymphocyte counts have normalized if longer than 6 months) of the baseline visit or the patient's prior patch testing, whichever is longer.
5. Treatment with topical corticosteroids, topical phosphodiesterase inhibitors or topical calcineurin inhibitors within 1 week before the baseline visit
6. Other active conditions, such as psoriasis, that may confound clinical evaluations of dermatitis and patient-reported symptoms.
7. Increased risk of infection or reactivated infection, including history of human immunodeficiency virus, hepatitis B, hepatitis C, endoparasitic infections, receipt of a live attenuated vaccine within 3 months of the baseline visit, chronic or acute infection requiring treatment within 4 weeks of the baseline visit, immunosuppressed status (ie recurrent or resistant opportunistic infections)
8. Malignancy within 5 years of the screening visit excluding local cutaneous squamous cell carcinoma, basal cell carcinoma or cervical carcinoma in situ that has been fully treated.
9. Women who are or plan to become pregnant or breastfeed during study participation or are unable or not willing to use birth control during the study and for 4 months after the last dose of dupilumab. Options for birth control include abstinence, double barrier (ie male condom and female diaphragm), vasectomy, intrauterine device, and hormonal contraception. Females who have not had menses within 1 year of the baseline, bilateral tubal ligation, hysterectomy, and/or bilateral oophorectomy visit do not require additional methods contraception during study participation.
10. Unstable condition or status, as per study investigator's judgment, that may lead to more likely discontinuation from the study including but not limited to major, recurrent medical illnesses that may require hospital admission and/or discontinuation of dupilumab, surgery that would require discontinuation of dupilumab and/or major rehabilitation, inability to participate in all study visits and administer dupilumab.
11. Resident outside of Massachusetts, Connecticut, Rhode Island, New Hampshire, Maine or Vermont state.
12. Unable to use Zoom videoconferencing.

#### **4.2.2 Discontinuation of Subjects from Treatment**

Patients may withdraw from the study for any reason and at any time and will not

be subject to consequences because of their withdrawal. The investigators may also withdraw a patient from the study for any reason such as to protect patient safety, administrative changes, or protocol deviation. Patients who withdraw or are withdrawn from the study will undergo early termination study assessments.

## **5 TREATMENTS**

### **5.1 Study Treatment: Dupilumab**

Patients will receive dupilumab subcutaneously 300 mg every 2 weeks during the 10-week treatment period following a loading dose of 600 mg at Week 0 +72-120 hours. The study staff will demonstrate to the patient administration of study drug at Week 0 +72-120 hours through Zoom video conference and will administer the first loading dose injection at the in-person portion of the visit on the same day. The study staff will observe the patient self-administer the second loading dose injection. After the initial dose dupilumab will be self-administered by patients off-site. Injection sites may include the four quadrants of the abdomen (avoiding the umbilicus and waist), upper thigh, and upper arms. The same site should not be injected for two consecutive doses of dupilumab. A dupilumab administration log will also be provided to patients.

#### **5.1.1 Identification**

Dupilumab injection is dispensed as a 300 mg/syringe (300 mg/2 mL) for subcutaneous administration, which contains L-arginine hydrochloride (10.5 mg), L-histidine (6.2 mg), polysorbate 80 (4 mg), sodium acetate (2 mg), sucrose (100 mg), and water for injection, pH 5.9.

#### **5.1.2 Packaging and Labeling**

Dupilumab SC is supplied in a box of 2 syringes with an open-label.

#### **5.1.3 Handling and Dispensing**

Dupilumab will be stored by the study pharmacy under refrigeration (approximately 2°C to 8°C).

## **5.2 Drug Ordering and Accountability**

### **5.2.1 Initial Orders**

Initial dupilumab orders will be placed through the Regeneron project manager.

### **5.2.2 Re-Supply**

Re-supply dupilumab orders will be placed through the Regeneron project manager.

## **5.3 Timing of Dose for Each Subject**

Two doses of dupilumab, 300 mg/2 mL, will be administered subcutaneously using the prefilled syringe at week 0 +72-120 hours and one dose dupilumab, 300 mg/2 mL, will be administered subcutaneously every two weeks thereafter continuing until week 10 +72-120 hours.

### **5.3.1 Dose Modifications**

Not applicable.

## **5.4 Blinding/Unblinding**

Not applicable.

## **5.5 Concomitant Treatments**

See inclusion and exclusion criteria (4.2.1 and 4.2.2) for details on concomitant treatments allowed and not allowed for study participation.

## **5.6 Treatment Compliance**

Patients will be given a dupilumab dosing diary that will be collected at the completion of the study to monitor treatment compliance.

# **6 STUDY ASSESSMENTS AND PROCEDURES**

## **6.1 Time and Events Schedule**

Time and events schedule is detailed in the table below:

Visit Number	1 Screening	2 Week 0	3 Week 0 +72-120 Hours	4 Week 6	5 12 Weeks	6 12 Weeks +72-120 hours	7 Early Termination /Unscheduled Visit
---------------------	------------------------	-------------------------	---	-------------------------	---------------------------	---	---

Day (+/- 3 days)	-34 to 0	1	4	42	84	87	N/A
Informed eConsent	X						
Inclusion/Exclusion Criteria	X						
Medical History	X						
Prior/Concurrent Medications	X						X
Safety Assessments							
Adverse Events		X	X	X	X	X	X
Clinical Efficacy Assessments							
Patch Test Site Reaction			X			X	
IGA	X	X		X	X		X
EASI		X		X	X		X
BSA		X		X	X		X
Patient-Reported Outcomes							
DLQI		X		X	X		X
NRS Itch		X		X			X
SLEEPYQ		X		X	X		X
Distribute Diaries (Allergen Avoidance and Dupilumab Dosing)		X					
Collect Diaries (Allergen Avoidance and Dupilumab Dosing)						X	X
Laboratory Assessments							
Pregnancy Test	X	X		X	X		X
Biomarker Skin Sample			X			X*	
Biomarker Serum Sample		X	X		X	X	
Medication Dosing							
In-Office Dosing			X				
Dispense Study Medication			X	X			
Patch Testing							
Patch Test Material Placement		X			X		
Patch Test Material Removal							
Photographs							
Patch Test Site Photographs		X	X		X	X	
Dermatitis Photographs			X			X	X

\*In addition to the allergen patch site and normal skin, an additional biopsy will be done on an area of persistent dermatitis if present unless in an anatomic location not amenable to biopsy (face, hands, elbows, knees, genitals, feet).

## 6.2 Study Materials

Dupilumab will be provided by Regeneron at no cost.

## 6.3 Safety Assessments

All subjects who receive a dose of dupilumab will be evaluated for safety. Our clinical trials team will provide periodic audits internally for safety assessments. The investigator will determine the severity of each adverse event as mild, moderate, severe, or very severe. The relationship between the adverse event and study drug will also be determined. Dupilumab may be discontinued due to lack of effectiveness, patient is lost-to-follow-up or withdraws consent, protocol deviation, or adverse event that may cause severe or permanent harm according to the judgment of the study investigator or an adverse event of grade 2 or more related to dupilumab defined by the National Cancer Institute Common Terminology Criteria for Adverse Events, Version 4.0 (CTCAE: [https://ctep.cancer.gov/protocoldevelopment/electronic\\_applications/ctc.htm](https://ctep.cancer.gov/protocoldevelopment/electronic_applications/ctc.htm)).

Notification will be provided to Regeneron if a patient discontinues dupilumab and the reason will be recorded in the patient's medical and study records.

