## **7.2 Collection and Reporting**

When documenting adverse events the diagnosis is preferable to symptoms. Information that should be collected for adverse events include: onset, duration, intensity, and seriousness of the event, relationship between the event and dupilumab, resulting action taken, and any required treatments (should be documented in the medical record).

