### **9.4.2 Safety Analyses**

Subjects will be questioned about experiencing any adverse events at every follow-up visit.

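### Four of the six dosing occasions have no scheduled adverse-event review since the previous dose, so the section 6.3 discontinuation provision relies on unprompted reports between visits

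*Combined protocol and SAP*

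**What the plan says.** Section 6.3 (Safety Assessments) says that dupilumab may be discontinued for, among other reasons, an event that in the investigator's judgment may cause severe or permanent harm, or "an adverse event of grade 2 or more related to dupilumab". Section 4.2.2 (Discontinuation of Subjects from Treatment) also allows withdrawal to protect the patient's safety.

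Section 5.3 gives the loading dose at Week 0 +72-120 hours; one 300 mg dose then "will be administered subcutaneously every two weeks thereafter continuing until week 10 +72-120 hours". Section 5.1 adds: "After the initial dose dupilumab will be self-administered by patients off-site".

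On detection, section 9.4.2 says: "Subjects will be questioned about experiencing any adverse events at every follow-up visit". The Adverse Events row of the schedule in section 6.1 is marked on Days 1, 4, 42, 84 and 87 and at early termination or unscheduled visits. The row "Dispense Study Medication" is marked only at Week 0 +72-120 hours and Week 6. The diaries cover allergen avoidance and dosing only, and section 5.6 describes a "dupilumab dosing diary that will be collected at the completion of the study". Section 7.2 asks staff to record, among other items, "onset, duration, intensity, and seriousness of the event".

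**The concern.** The discontinuation provision can work only if staff hear of an event before the next injection. Most injections are given at home, and the plan schedules one adverse-event review (Week 6) between the first and last dose. No later hand-over of drug brings staff and subject together before the doses on Days 60 and 74, and the diary neither asks about symptoms nor reaches staff until the end.

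Two things are at stake. A subject with an event that meets section 6.3 may keep injecting unless he or she thinks to report it. And onset, duration and intensity would rest on recall over as much as six weeks, which favours under-recording of non-serious events.

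**Working it through.** **Inputs**

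- Dosing: first occasion nominally Day 4 (6.1), then every 14 days to Week 10 +72-120 hours (5.3).
- Adverse-event reviews: Days 1, 4, 42, 84, 87 (6.1).
- Visit window: ±3 days (6.1).

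**Plan's own dose count.** The synopsis gives 7 doses over 10 weeks. Two 300 mg syringes at loading plus five later doses make 7, and the first-to-last interval is 5 × 14 = 70 days. The figure reproduces. It counts 300 mg units, which fall on six dosing occasions.

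**Dose days.** 4 + 14k for k = 0 to 5 gives Days 4, 18, 32, 46, 60, 74.

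**Scheduled review since the previous dose?**

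| Dose day | Review |
|---|---|
| 4 | Yes (same-day visit; no previous dose) |
| 18 | No |
| 32 | No |
| 46 | Yes (Day 42) |
| 60 | No |
| 74 | No |

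Four of six have none. The gaps between reviews are 42 − 4 = 38 days and 84 − 42 = 42 days.

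**Sensitivity to windows.** The first dose was moved over Days 4-6, the Week 6 visit over Days 39-45, and the later doses 0-6 days earlier: 3 × 7 × 7 = 147 combinations. The count stays at four of six in all of them. In 116 the unreviewed doses are Weeks 2, 4, 8 and 10. In 31, where the Week 6 visit falls after the Week 6 dose, they are Weeks 2, 4, 6 and 10.

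**Further doses before the next scheduled review, by day of onset**

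| Onset (days) | Length | Next review | Further doses |
|---|---|---|---|
| 4-18 | 14 | 42 | 2 |
| 18-32 | 14 | 42 | 1 |
| 32-42 | 10 | 42 | 0 |
| 42-46 | 4 | 84 | 3 |
| 46-60 | 14 | 84 | 2 |
| 60-74 | 14 | 84 | 1 |

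- Days with at least one further dose: 14 + 14 + 4 + 14 + 14 = 60 of 70.
- Days with two or three: 14 + 4 + 14 = 32 of 70.
- Mean, for onset uniform over the 70 days: (14×2 + 14×1 + 10×0 + 4×3 + 14×2 + 14×1)/70 = 96/70 = 1.37.
- From the last dose to the next review: 84 − 74 = 10 days.

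**With a check before the doses on Days 18, 32, 60 and 74.** Only onset in Days 42-46 is still followed by a dose (Day 46) before a check, so the exposed days fall to 4 of 70 and the mean to 4×1/70 = 0.06. The gaps from Day 4 become 14, 14, 10, 18, 14 and 10 days, with a maximum of 18.

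**Illustration of scale only.** Section 1.3.3.1 reports conjunctivitis at 20 per 100 subject-years on dupilumab with topical corticosteroid and 10 per 100 on placebo with topical corticosteroid, an excess of 10 per 100, in a 52-week trial. Expected cases starting in Days 42-74 (32 days) = rate × 32/365.25 × n, and P(at least one) = 1 − exp(−expected).

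| Treated | Rate per year | Expected cases | P(at least one) |
|---|---|---|---|
| 30 | 0.20 | 0.53 | 41% |
| 30 | 0.10 (excess) | 0.26 | 23% |
| 14 | 0.20 | 0.25 | 22% |
| 14 | 0.10 (excess) | 0.12 | 12% |

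These assume a constant rate and cover all grades.

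**The case against.** The schedule itself is not in dispute; the case against concerns its weight.

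- **Discretion.** Section 6.3 is permissive, and nothing in the protocol promises a review before each dose. That is right: this is a design choice that can be improved, and no rule is broken.
- **Existing safeguards.** The plan has unscheduled visits with adverse-event review, 24-hour reporting of serious events to the manufacturer (7.2.1), follow-up of non-serious events until resolved or stable (7.2.2), internal audits (6.3) and virtual visits (4.1). Reporting and follow-up act only once staff know of the event. Nothing scheduled triggers an unscheduled visit, and the audits and virtual visits add no dated contact with the subject.
- **Unseen instructions.** The administration log in section 5.1 is not shown, and the consent pages were not available. Subjects may be told there when to call. This stands as a limit: one can say that no contact or diary item prompting a report is scheduled, but not that subjects receive no instruction.
- **Opportunity, not harm.** The day and dose counts become missed stops only if the event goes unreported and the investigator would have stopped. Related, unreported events of grade 2 or more must be fewer than the conjunctivitis figures suggest, and the documents give no inputs to estimate them. This also stands.
- **Benefit of stopping.** Section 1.3.2 gives a median of 10 weeks to non-detectable concentration after the last steady-state dose on the two-weekly regimen, so omitting a late dose lowers exposure only gradually. That limits the gain but does not remove the reason for having the provision.
- **Low-risk setting.** This is a short open-label pilot of an approved drug, and safety is not a stated objective. That argues for a light remedy, such as the one proposed.

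**Conclusion.** The concern holds. Four of the six dosing occasions have no scheduled adverse-event review since the previous dose, and this count does not change across the visit windows examined. The Week 6 visit can still stop the last three doses for events that began by then. For events that start later, the next scheduled question comes when no dose is left to withhold.

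The 1.4-dose average assumes onset spread evenly between the first and last dose, and no spontaneous report. It measures how long the provision is without a scheduled trigger; it does not estimate harm. The conjunctivitis figures come from another population and the finding does not depend on them. The issue bears on patient safety and on the completeness of adverse-event data. It should be corrected because the remedy is cheap, but the trial could run without it.

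**What to change.** 1. Add an adverse-event item with onset date to the existing dosing diary, to be completed before each off-site injection, with an instruction to contact staff before injecting if the answer is positive. This is the most important of the three and is worth making on its own.
2. Have existing staff make a short Zoom or phone check before the doses on nominal Days 18, 32, 60 and 74. The Week 6 visit serves the Day 46 dose. If that visit slips past the dose, the diary item covers it.
3. Mark these contacts in the Adverse Events row of section 6.1.

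Which events stop treatment stays with the investigator, as section 6.3 now has it.

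The cost is one diary line, one schedule change and up to four brief remote contacts per subject, at most 4 × 30 = 120 in all. Every subject must already be able to use Zoom, and at about one enrolment per month few are on drug at once. The downsides are a little staff time and more non-serious events to record. No clinic visit, procedure, committee or sample-size change is needed.

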## **6.4 Efficacy Assessments**

### **6.4.1 Primary Efficacy Assessment**

The following clinical assessments will provide outcome data:

Number of patients who achieve a reduction in patch test site reactions from 2+-3+ at baseline to "?" or no reaction at week 12 +72-120 hours.

### **6.4.2 Secondary Efficacy Assessments**

#### **6.4.2.1 Secondary Clinical Endpoints**

Secondary endpoint 1: Number of patients who achieve a reduction in investigator global assessment (IGA) from 3 or greater at screen and baseline to 0 or 1 at Week 6, and Week 12.

Secondary endpoint 2a: To quantify the inflammatory markers (Th1, Th2, Th17, Th22 immune pathways) in the blood and skin of patients before and after dupilumab. Secondary endpoint 2b: Changes in IGA from baseline to week 12. Other secondary endpoints: Change in baseline eczema-area-and-severity-index (EASI), body surface area (BSA), numerical rating scale (NRS) itch, dermatology life quality index (DLQI), and SLEEPYQ from baseline to Week 6 and Week 12.

Secondary endpoint 3: Changes in IGA from baseline to Week 6 and Week 12.

Other secondary endpoints: Change in baseline eczema-area-and-severity-index (EASI), body surface area (BSA), numerical rating scale (NRS) itch, dermatology life quality index (DLQI), and SLEEPYQ from baseline to Week 6 and Week 12.

Secondary endpoint 4: Identification and quantification of the most prevalent T cell clones in the skin before therapy and how those clones change after therapy using high-throughput sequencing of the TCRB gene.

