### **2.2 Secondary Objectives**

Secondary endpoint 1: Number of patients who achieve a reduction in investigator global assessment (IGA) from 3 or greater at screen and baseline to 0 or 1 at Week 6 and Week 12.

Secondary endpoint 2a: To quantify the inflammatory markers (Th1, Th2, Th17, Th22 immune pathways) in the blood and skin of patients before and after dupilumab. Using novel nanostring-based gene expression assays and multispectral immunofluorescence we will quantify changes in key genes that are specific for the Th1, Th2, Th17, Th22 immune pathways in the skin and blood of patients before and after treatment with dupilumab. Secondary endpoint 2b: Changes in IGA from baseline to week 12. Other secondary endpoints: Change in baseline eczema-area-and-severity-index (EASI), body surface area (BSA), numerical rating scale (NRS) itch, dermatology life quality index (DLQI), and SLEEPYQ from baseline to Week 6 and Week 12.

Secondary endpoint 3: To measure the reductions in the severity of clinical skin disease and quality of life scores with dupilumab treatment. We will measure changes in investigator global assessment (IGA; scored on a scale of 0-5 with 0 being no disease and 5 being the most severe disease) from baseline to Week 6 and Week 12.

Secondary endpoint 4: To address whether dupilumab affects T cell trafficking, use high-throughput sequencing of the T-cell receptor (TCR HTS) to identify the unique

CDR3 sequence of the likely pathogenic T cell clones before therapy and quantify their relative frequency in the skin after dupilumab therapy.

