We will recruit 30 patients with allergic contact dermatitis 18 years of age and older up to 6 months after patch testing with a documented IGA of at least 3 at baseline and screening visits, and at least one 2+ (strong) or 3+ (extreme) reaction on patch testing to participate in this open-label pilot study. If more than one 2+ (strong) or 3+ (extreme) reactions are present, up to two may be selected for evaluation in the study. Priority will be given to nickel, fragrance mix I or II, and rubber as these allergens have been studied previously with respect to their preferential T helper cell skewing. At the initial screening visit, demographic information will be obtained, inclusion and exclusion criteria as detailed in Section 4.2 will be reviewed, and informed consent obtained for those deemed eligible for enrollment. A single subcutaneous dose of 600 mg will be self-administered at week 0 +72-120 hours and 300 mg every 2 weeks thereafter for a total 10 weeks of therapy. Subjects will be evaluated for improvement in primary and secondary endpoints using clinical examination and questionnaires during initial and follow-up visits at Week 0, Week 6, and Week 12 as per Time and Events Schedule. Patch test site reactions will also be evaluated 72 hours after the Week 0 and Week 12 visits. Skin biopsies will be taken at these two time points from both the patch test site reaction and from normal skin taken from a non-dermatitic area on the contralateral side of the body. For the Week 12 patch placement, a site contralateral to the Week 0 patch placement site will be chosen. If an area of persistent dermatitis other than the patch test site(s) is also present at week 12+72-120 hours an additional biopsy will be taken unless in an anatomic location not amenable to biopsy (face, hands, elbows, knees, genitals, feet). Serum samples will be obtained at four time-points including Week 0 (prior to patch placement), Week 0 +72-120 hours, Week 12 (prior to patch placement), and Week 12 +72-120 hours. If subjects do not mount a 2+ (strong) or 3+ extreme reaction to the tested allergens at the Week 0 +72-120 hour visit they will be discontinued from the study and will not receive dupilumab. These patients will be considered screen fails. Week 10 +72-120 hours will conclude the end of the treatment portion of the study. Week 12 +72-120 hours will conclude the subjects' participation in the study.

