## **9.3 Endpoint Definitions**

Investigator's Global Assessment (IGA) score

The investigator's global assessment is a physician-reported global assessment of disease activity (range 0-4) with 0 being clear and 4 being severe.

Body Surface Area (BSA)

The body surface area is a physician-reported measure of the amount of disease involvement. The patient's palm size approximates 1% of body surface area involvement.

Eczema Area and Severity Index (EASI) score

The eczema-area-and-severity-index score is a composite score of disease severity and extent of disease distribution. It was initially developed for evaluation of eczema. Disease severity (range 0-3; 0 being no disease and 3 being severe disease) is a measure of redness, thickness/induration, scratching, and lichenification. Each characterization is measured separately for body regions (head and neck, trunk, upper extremities, and lower extremities) to calculate a regional score. The total score is a sum of the four body regions (range 0-72).

Numerical Rating Scale (NRS) itch

The numerical rating scale for itch is a patient-reported measure of itch (range 0-10) with 0 being no itch and 10 being the worst imaginable itch.

Dermatology Life Quality Index (DLQI)

The Dermatology Life Quality Index is a 10-question, patient-reported instrument to assess impact of skin diseases on patient quality of life.

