The primary clinical efficacy endpoint will be the number of patients who achieve a reduction in patch test site reactions from 2+-3+ at baseline to "?" or no reaction at week 12 +72-120 hours. Secondary endpoints will include number of patients who achieve a reduction in investigator global assessment (IGA) from 3 or greater at screen and baseline to 0 or 1 at Week 6, and Week 12; quantification of the inflammatory markers (Th1, Th2, Th17, Th22 immune pathways) in the blood and skin of patients before and after dupilumab; changes in IGA from baseline to week 12. Other secondary endpoints: Change in baseline eczema-area-and-severity-index (EASI), body surface area (BSA), numerical rating scale (NRS) itch, dermatology life quality index (DLQI), and SLEEPYQ from baseline to Week 6 and Week 12; changes in IGA from baseline to Week 6 and Week 12; changes in baseline eczema-area-and-severity-index (EASI), body surface area (BSA), numerical rating scale (NRS) itch, dermatology life quality index (DLQI), and SLEEPYQ from baseline to Week 6 and Week 12; identification and quantification of the most prevalent T cell clones in the skin before therapy and how those clones change after therapy using high-throughput sequencing of the TCRB gene.

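### Itch change at Week 12 is a listed secondary endpoint, but the visit schedule has no NRS itch assessment at Week 12

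*Combined protocol and SAP*

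**What the plan says.** Four places define the itch endpoint at two time points: the synopsis, Section 2.2, Section 6.4.2.1 and Section 9.4.3. Section 6.4.2.1 asks for change in "numerical rating scale (NRS) itch, dermatology life quality index (DLQI), and SLEEPYQ from baseline to Week 6 and Week 12". Section 9.4.3 repeats it: "numerical rating scale (NRS) itch, dermatology life quality index (DLQI), and SLEEPYQ from baseline to Week 6 and Week 12; changes in IGA".

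The Time and Events Schedule in Section 6.1 has seven visit columns. The NRS itch row is marked at Visit 2 (Week 0), Visit 4 (Week 6) and Visit 7, headed "Early Termination /Unscheduled Visit". Visit 5 (Week 12) and Visit 6 (Week 12 +72-120 hours) are blank.

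Section 4.1 describes clinical examination and "questionnaires during initial and follow-up visits at Week 0, Week 6, and Week 12 as per Time and Events Schedule". On the end of dosing it says: "Week 10 +72-120 hours will conclude the end of the treatment portion of the study".

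On a separate matter, Section 2.2 describes the IGA as "scored on a scale of 0-5 with 0 being no disease and 5 being the most severe disease". Inclusion criterion 4 in Section 4.2.1 requires a "score of at least 3 (range 0-4) at the screening and baseline visits", and Section 9.3 defines a "physician-reported global assessment of disease activity (range 0-4) with 0 being clear and 4 being severe".

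**The concern.** The schedule is what site staff work from. If they follow it, the Week 12 half of the itch endpoint has no planned data. The only scheduled itch score after baseline would be at Week 6, part-way through dosing, so the study would not show what happens to itch after the full course.

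The one later opportunity is the early-termination or unscheduled visit. The section on discontinuation ties early-termination assessments to patients who withdraw or are withdrawn, and Section 6.3 names lack of effectiveness and adverse events among the reasons for stopping. Scores from that visit come from a selected group and cannot stand in for completers. Section 9 gives no rule for missing data that would bridge the gap.

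The IGA conflict matters less. One instrument serves for entry, response and change, and it should have one stated range.

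**Working it through.** No sample-size or power formula applies. The check sets the endpoint list against the schedule.

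**Step 1: marks in Section 6.1.** Each row below has seven cells for the seven visits, so no column has shifted.

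| Measure | Visits marked | Week 6 (Visit 4) | Week 12 (Visit 5) |
|---|---|---|---|
| IGA | 1, 2, 4, 5, 7 | yes | yes |
| EASI | 2, 4, 5, 7 | yes | yes |
| BSA | 2, 4, 5, 7 | yes | yes |
| DLQI | 2, 4, 5, 7 | yes | yes |
| NRS itch | 2, 4, 7 | yes | **no** |
| SLEEPYQ | 2, 4, 5, 7 | yes | yes |

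Five of the six repeated measures are marked at Week 12; NRS itch is the exception.

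**Step 2: coverage of the planned change scores.** The other secondary endpoints cover five measures (EASI, BSA, NRS itch, DLQI, SLEEPYQ) at two time points: 5 × 2 = 10 change scores. Week 6 is covered for 5 of 5 and Week 12 for 4 of 5, so 5 + 4 = 9 of 10 have a scheduled assessment.

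**Step 3: patients affected.** Section 9.1 needs at least 14 completers and enrols at most 30. With no mark at Visit 5 or 6, the number of scheduled Week 12 itch scores is 0 whatever the number of completers.

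**Step 4: where Week 6 falls in the course.** Section 6.1 puts the first dosing visit at Day 4, and Section 5.3 gives a dose every two weeks up to Week 10 +72-120 hours. The nominal dosing days are 4, 18, 32, 46, 60 and 74. The Week 6 visit is Day 42, or Day 45 at the end of its 3-day window. It therefore follows 3 of 6 dosing occasions. The Week 12 visit, Day 84, follows all six.

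**Step 5: does the narrative supply the assessment?** Section 4.1 names Week 12 for questionnaires but makes the timing subject to the schedule, as does the synopsis. It supports the intention to collect itch at Week 12 but does not add the assessment.

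**Step 6: IGA range.** Section 2.2 gives 0-5. The synopsis inclusion criteria, Section 4.2.1 and Section 9.3 give 0-4. The IGA endpoints can be computed on the 0-4 scale.

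**The case against.** The strongest reply is that this is a missed mark and the intention is plain. Four endpoint statements name Week 12, the other five instruments are all marked there, and Section 4.1 says the secondary endpoints are evaluated by questionnaire at that visit. A sensible site might collect the score anyway. The same table leaves the row for removing patch test material blank at every visit, although patches are placed at Week 0 and Week 12, so an empty cell is weak evidence of a deliberate choice. An intact count of seven cells excludes a shifted column but not one mark lost in converting the table to text.

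Much of this stands. A clerical omission is the likeliest explanation, and the published table should be looked at to confirm the blank. It is also fair that this is one lower-tier endpoint in an open-label, single-arm pilot, with no test or power attached to it.

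None of it removes the contradiction. The narrative defers to the table, so the blank cell is the operative instruction, and an accidental blank loses the same data as a deliberate one. The IGA range is an editorial slip and adds nothing to the weight of the itch point.

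**Conclusion.** The concern holds. The endpoint lists and the schedule contradict each other on NRS itch at Week 12. Followed as written, the schedule leaves one of the ten other secondary change scores without planned data in every completer, and leaves no scheduled itch score after the full course. The Week 6 itch change can be computed, and the primary endpoint and its power are untouched.

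This rests on two assumptions: that the blank at Visit 5 is in the protocol's own table, and that sites follow the table. It is an internal inconsistency of modest weight that should be corrected, because an uncollected patient-reported score cannot be obtained afterwards. The IGA discrepancy is real but minor.

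**What to change.** In Section 6.1, mark NRS itch at Visit 5, as is already done for DLQI and SLEEPYQ. The cost is one mark in the table and one 0-10 item at a visit that already takes place. The change needs to be in force before Week 12 visits are held.

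The alternative is to limit the itch endpoint to Week 6 in the synopsis and Sections 2.2, 6.4.2.1 and 9.4.3. That would also make the document consistent, but it gives up the only planned itch measurement after the full course, and the endpoint statements favour adding the mark.

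In Section 2.2, replace the 0-5 IGA range with the 0-4 range and anchors in Section 9.3. That is one line of text.
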